**Table 2 Visit Windows for Unscheduled and Early Termination Assessments or Measurements**

Study Period	Adjusted-Defined Windows Visit	Scheduled Period Day	Visit Windows				
			ESS, SF-36 and EQ-5D-5L	Clinical Laboratory: Hematology and Chemistry A , ECG, CGIc and PGIc B	Electrolytes	PHQ-9	C-SSRS, Weight, Vital Signs and Urine Drug Screen
OL OTTP	End of Week 1	8	n/a	n/a	n/a	n/a	Study Day 1 < Period Day ≤ 18
	End of Week 2	15	n/a	n/a	n/a	Study Day 1 < Period Day ≤ 22	n/a
	End of Week 4	29	n/a	n/a	Study Day 1 < Period Day ≤ 43	23 ≤ Period Day ≤ 36	19 ≤ Period Day ≤ 43
	End of Week 6	43	n/a	n/a	n/a	37 ≤ Period Day ≤ 43	n/a
	End of Week 8	57	n/a	n/a	44 ≤ Period Day ≤ 71	44 ≤ Period Day ≤ 50	44 ≤ Period Day ≤ 71
	End of Week 10	71	n/a	n/a	n/a	51 ≤ Period Day ≤ 64	n/a
	End of OL OTTP (End of Week 12)	85	n/a	n/a	72 ≤ Period Day ≤ Date of Visit 14	65 ≤ Period Day ≤ Date of Visit 14	72 ≤ Period Day ≤ Date of Visit 14
OL SDP	End of OL SDP (End of Week 14)	15	Study Day 1 < Period Day ≤ Date of Visit 15	n/a	1 < Period Day ≤ Date of Visit 15	1 < Period Day ≤ Date of Visit 15	1 < Period Day ≤ Date of Visit 15
DB RWP	End of DB RWP (End of Week 16)	15	1 < Period Day ≤ Date of Visit 16	Study Day 1 < Period Day ≤ Date of Visit 16	1 < Period Day ≤ Date of Visit 16	1 < Period Day ≤ Date of Visit 16	1 < Period Day ≤ Date of Visit 16
OLE	End of OLE Week 12	85	n/a	n/a	1 < Period Day ≤ Date of Visit 33	1 < Period Day ≤ 127	1 < Period Day ≤ 127
	End of OLE Week 24	169	n/a	1 < Period Day ≤ Date of Visit 33	n/a	128 ≤ Period Day ≤ Date of Visit 33	128 ≤ Period Day ≤ Date of Visit 33

A Exception of electrolytes (i.e., sodium, potassium, magnesium, and calcium) and TSH (screening only).

B CGIc and PGIc are not collected during OLE

Note: CGIc: Clinician Global Impression of Change. C-SSRS: Columbia-Suicide Severity Rating Scale. DB: Double-Blind. ECG: Electrocardiogram. ESS: Epworth Sleepiness Scale. EQ-5D-5L: European Quality of Life 5 Dimensions 5 Levels. n/a: Not Applicable. OL: Open-Label. OLE: Open-Label Extension. OTTP: Optimized Treatment and Titration Period. PGIc: Patient Global Impression of Change. PHQ-9: Patient Health Questionnaire-9. RWP: Randomized-Withdrawal Period. SDP: Stable-Dose Period. SF-36: 36-Item Short Form Health Survey. TSH: Thyroid Stimulating Hormone.

Note: Period Day 1 and first dose of study drug of a study period are excluded from the visit windows as the study drug will be taken only after all the assessments scheduled to be collected on these days will have been performed.

If multiple assessments or measurements are recorded within a single visit window (including unscheduled, repeated, and retest assessments or measurements as well as early discontinuation data), the following rules will be applied to determine the result from which assessment or measurement will be used for the summaries for that visit window.

- If there are two or more results within the same visit window, then the non-missing one closest to the scheduled Period Day will be used in the analysis.
- If two observations are equidistant from the scheduled Period Day, then the non-missing observation with the earliest collection date will be used in the analysis.
- If two observations are collected on the same day and this day is the closest to the scheduled Period Day, then the non-missing observation with the earliest collection time will be included in the analysis.

If a visit window does not contain any observations, then the data will remain missing.

Listings will include scheduled, unscheduled, repeated, retest, and early termination data.

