**Table 1 Visit Windows for Assessments Recorded Daily**

Study Period	Adjusted-Defined Windows		Visit Windows
	Visit	Scheduled Period Day	
OL OTTP	Week 1	8	Study Day 1 < Period Day ≤ 8
	Week 2	15	9 ≤ Period Day ≤ 15
	Week 3	22	16 ≤ Period Day ≤ 22
	Week 4	29	23 ≤ Period Day ≤ 29
	Week 5	36	30 ≤ Period Day ≤ 36
	Week 6	43	37 ≤ Period Day ≤ 43
	Week 7	50	44 ≤ Period Day ≤ 50
	Week 8	57	51 ≤ Period Day ≤ 57
	Week 9	64	58 ≤ Period Day ≤ 64
	Week 10	71	65 ≤ Period Day ≤ 71
	Week 11	78	72 ≤ Period Day ≤ 78
	Week 12	85	79 ≤ Period Day ≤ Date of Visit 14

Statistical Analysis Plan

---

OL SDP	Week 1	8	1 < Period Day ≤ 8
	Week 2	15	9 ≤ Period Day ≤ Date of Visit 15
	Over Weeks 1 and 2	n/a	1 < Period Day ≤ Date of Visit 15
DB RWP	Week 1	8	1 < Period Day ≤ 8
	Week 2	15	9 ≤ Period Day ≤ Date of Visit 16
	Over Weeks 1 and 2	n/a	1 < Period Day ≤ Date of Visit 16

Note: DB: Double-Blind. n/a: Not Applicable. OL: Open-Label. OTTP: Optimized Treatment and Titration Period. RWP: Randomized-Withdrawal Period. SDP: Stable-Dose Period.

Note: Period Day 1 is excluded from the visit windows as the study drug will be taken only after all the assessments scheduled to be collected on that day will have been performed.

Note: For SDP longer or shorter than 14 days, use all available data from the period to calculate baseline, for DB RWP longer or shorter than 14 days, use all available data to account for efficacy.

For measurements/assessments other than cataplexy attacks, scheduled assessments will be summarized by nominal visits. Unscheduled and Early Termination visits will be mapped based on the scheduled Period Day of each visit with adjusted analysis-defined visit windows, unless otherwise specified. The adjusted analysis-defined windows are specified in [Table 2](#).

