### 9.9.5.2. PATIENT HEALTH QUESTIONNAIRE-9

The PHQ-9 is a nine-item depression scale developed based on the nine diagnostic criteria for major depressive disorder in the Diagnostic and Statistical Manual Fourth Edition (DSM-IV) (Kroenke *et al* 2001, Kroenke *et al* 2010). Responses to each item range from 0 = not at all to 3 = nearly every day. The instrument can be administered in person, by telephone or can be self-administered and is used to facilitate diagnosis of major depression and assessment of symptom severity. The PHQ-9 will be assessed at Main Study screening visit, start of the OL OTTP visit (day 1), week 2, week 4, week 6, week 8, week 10, end of OL OTTP visit (week 12), end of OL SDP visit (week 14), end of DB RWP/ Early Termination visit (week 16), Main Study Safety Follow-up visit (week 18), OLE screening visit, OLE week 12, end of OLE/Early Termination visit (OLE week 24), and OLE Safety Follow-up visit (week 26).

The PHQ-9 total score is the sum of 9 item-scores and can range between 0 and 27 with higher scores indicating greater severity of depression (1-4 = minimal depression; 5-9 = mild depression; 10-14 = moderate depression; 15-19 = moderately severe depression; and 20-27 = severe depression). If 3 or

more items are left unanswered, the total score will not be computed. If 1 or 2 items are left unanswered, a prorated score will be calculated. The prorated score is calculated as the sum of the scores of the items that were answered to get a partial raw score. Then, the partial raw score will be multiplied by the total number of items on the PHQ-9 (i.e., 9) and divided by the number of items that were actually answered (i.e., 7 or 8). If the result is a fraction, it will be rounded to the nearest whole number.

PHQ-9 total score and change from baseline (Main Study baseline and OLE baseline) will be tabulated by visit across all study periods by pre-randomization group and by treatment group.

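### SAP Table 2: the PHQ-9 windows for Weeks 8 and 10 miss their own scheduled days and OLE electrolytes have no Week 24 window, so some Early Termination and unscheduled safety records are tabulated at the wrong visit or drop out

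*SAP*

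**What the plan says.** SAP 6.3 sets two rules for everything except the cataplexy diary. First, "scheduled assessments will be summarized by nominal visits". Second, "Unscheduled and Early Termination visits will be mapped based on the scheduled Period Day of each visit", using the windows in Table 2. When a window holds several results, "then the non-missing one closest to the scheduled Period Day will be used in the analysis". For an empty window the rule is: "If a visit window does not contain any observations, then the data will remain missing".

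In the PHQ-9 column of Table 2, the titration-period windows from Week 6 on are:
- Week 6 (scheduled Day 43): 37 to 43
- Week 8 (scheduled Day 57): "44 ≤ Period Day ≤ 50"
- Week 10 (scheduled Day 71): "51 ≤ Period Day ≤ 64"
- Week 12 (scheduled Day 85): "65 ≤ Period Day ≤ Date of Visit 14"

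SAP 9.9.5.2 says that the PHQ-9 total score and its change from baseline "will be tabulated by visit across all study periods by pre-randomization group and by treatment group".

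In the electrolytes column, the OLE Week 12 row (Day 85) runs from after Day 1 to Visit 33, and the Week 24 row (Day 169) is not applicable. Footnote A takes sodium, potassium, magnesium and calcium out of the chemistry column, which does have a Week 24 window. SAP 9.9.2 nevertheless plans electrolyte results at the end of the OLE, and Protocol 7.2.3 collects these four analytes at Visit 33 or ET.

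**The concern.** A visit window should contain the day on which its visit is scheduled. Two PHQ-9 windows do not, and a third is cut short on its scheduled day. Programmed as printed, an ET score taken on the Week 8 day is shown as Week 10, and one taken on the Week 10 day as Week 12. The Week 8 or Week 10 cell then stays empty although a score from that time exists.

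For OLE electrolytes, a late ET sample has no end-of-OLE window to go to. The other chemistry results from the same blood draw are assigned to Week 24.

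These records will arise. Protocol 6.14.2 asks everyone who terminates early to have the final-visit assessments, which include the PHQ-9 and chemistry. The PHQ-9 is the protocol's measure of emergent depression, and electrolytes have their own by-visit summaries and a box plot. What is at stake is the accuracy of those descriptive safety tables.

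**Working it through.** **PHQ-9 windows.** Scheduled Period Day = 7 × week + 1. This reproduces the days in Table 2: Week 6 = 43, Week 8 = 57, Week 10 = 71, Week 12 = 85, OLE Week 24 = 169. The midpoint cut between two visits is the mean of their scheduled days, with a tie going to the earlier visit.

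| Visit | Scheduled day | Printed window | Contains own day? | Midpoint window |
|---|---|---|---|---|
| Week 2 | 15 | 2-22 | yes | 2-22 |
| Week 4 | 29 | 23-36 | yes | 23-36 |
| Week 6 | 43 | 37-43 | yes (last day) | 37-50 |
| Week 8 | 57 | 44-50 | no | 51-64 |
| Week 10 | 71 | 51-64 | no | 65-78 |
| Week 12 | 85 | 65 to Visit 14 | yes | 79 to end |

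The midpoint rule is the table's own. Titration electrolytes are cut at (29 + 57)/2 = 43 and (57 + 85)/2 = 71. The C-SSRS and vital-signs column adds (8 + 29)/2 = 18.5, printed as 18. The OLE cut for PHQ-9 and vital signs is (85 + 169)/2 = 127. Only the PHQ-9 cuts at 43, 50 and 64 break the rule. The printed windows run on without gaps, so a broken table is not the explanation. The printed Week 10 window is exactly the midpoint window for Week 8, which looks like a slip of one row.

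**Days affected.** Going through Days 2 to 85, the printed visit is not the nearest on:
- Days 44-49: sent to Week 8, nearest Week 6 (6 days)
- Days 51-63: sent to Week 10, nearest Week 8 (13 days)
- Days 65-77: sent to Week 12, nearest Week 10 (13 days)

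That is 6 + 13 + 13 = 32 of 84 days. Days 50, 64 and 78 are ties that the midpoint convention gives to the earlier visit, so the two sets of windows differ on 35 days. The same check finds no misplaced day in the titration electrolyte or C-SSRS columns, or in the OLE PHQ-9 column.

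**What midpoint windows do to an ET score.** Suppose all earlier PHQ-9s were on time.
- Days 51-57 and 65-71 (14 days): the corrected window holds no earlier scheduled score, so the ET score fills it. Its distance from the labelled visit falls from 14-20 days (mean 17) to 0-6 days (mean 3).
- Days 44-50, 58-64 and 72-78 (21 days): the corrected window already holds an on-time scheduled score. The closest-day rule keeps that score, and the ET score appears only in the listings. As printed, it is tabulated 7-13 days (mean 10) ahead of the scheduled day of the visit it is labelled with.

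**OLE electrolytes.** Days 128 to 169 (169 − 128 + 1 = 42 days) are nearer Day 169 than Day 85. Their mean distance is (43 + 84)/2 = 63.5 days from Day 85 and (0 + 41)/2 = 20.5 days from Day 169. As printed, they fall in the Week 12 window. With a Visit 30 sample on Day 85, the closest-day rule discards the later one; without one, the later sample is shown as Week 12.

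**The case against.** The strongest objection concerns the remedy. As printed, an ET PHQ-9 score on Days 44-78 is labelled late but does reach the table, because the next visit's slot is empty. Midpoint windows would move it to the listings on 21 of 35 days, and for a depression scale that may be worse than a label 7-13 days off. This stands. One route to an ET visit lies in that range: Protocol 7.1.2.3 calls for an ET visit when a Group 2 or 3 subject is still on an anticataplectic at Week 10, and a visit in the following week falls on Days 72-78. Correcting the windows without an ET row would therefore exchange one loss for another.

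The second objection concerns missed visits. A late Week 10 call recorded as Visit 12 keeps its nominal label, because SAP 6.3 sets no lateness limit. The 3-day allowance in Protocol Appendix 1.1 does not turn it into an unscheduled record. This also stands. Only a record logged as unscheduled is affected: on Day 75, for example, it would lose to the Day 85 score and leave Week 10 missing.

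Three stronger readings are tempting, and the documents do not support them:
- That Week 8 and Week 10 PHQ-9 data in general are misplaced. Scheduled assessments are summarized by nominal visit.
- That end-of-OLE electrolytes are lost. Scheduled Visit 33 samples keep their label.
- That Protocol Appendix 1.2 contradicts Protocol 7.2.3 because its electrolytes row is unmarked at Visit 33. The same schedule marks fasting chemistry there, and the chemistry panel in Protocol 6.10.1 includes all four electrolytes.

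**Conclusion.** The point holds as a minor error in SAP Table 2. Programmed as printed, the PHQ-9 column contradicts the mapping rule in SAP 6.3 on 32 Period Days, with 3 further days tied. The electrolytes column gives ET or unscheduled samples on 42 OLE days no Week 24 window, although SAP 9.9.2 plans an end-of-OLE result.

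These are counts of days, not of records. The plan expects about 55 subjects (185 − 130) to leave before randomization, but it does not say when, so the number of affected records is unknown. The 14 and 21 day counts assume that earlier PHQ-9s were on time, and the displacement of late OLE samples assumes an on-time Visit 30.

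Only descriptive safety tables are touched. All records stay in the listings, and no efficacy endpoint, test or error rate changes.

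**What to change.** Edit SAP Table 2 before programming:
- **PHQ-9 windows:** Week 6, Days 37-50; Week 8, 51-64; Week 10, 65-78; Week 12, from 79 to the end of the titration period. Define that end as Visit 14, or the ET visit for a subject who has no Visit 14, since the printed bound is undefined for someone who leaves during titration.
- **PHQ-9 output:** in the same edit, add an Early Termination row to the by-visit table in SAP 9.9.5.2, so that no ET score is left only in the listings.
- **OLE electrolytes:** Week 12, after Day 1 to Day 127; Week 24, Day 128 to Visit 33. PHQ-9 and vital signs already use this split.

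One difference remains: for an ET before OLE Day 128, electrolytes go to Week 12 while the other chemistry goes to Week 24, because the chemistry column has a single OLE window.

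The cost is a few table cells, one row in a table shell and a change to the windowing program. Data collection does not change.

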## 9.9. SAFETY OUTCOMES

In general, safety outcomes will be summarized across all study periods by visit overall, and by Pre-Randomization Group based on SAF. Data collected while subjects randomized to placebo were on placebo will be excluded from this summaries.

Data will also be summarized overall and by treatment group based on the DB RWP SAF.

No inferential statistics will be performed; only summary statistics will be provided unless otherwise noted.

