## 9.9.2. LABORATORY EVALUATIONS

Results from the central laboratory will be included in the reporting of this study for:

- **Hematology, Serum chemistry (excluding electrolytes):** Main Study baseline, end of DB RWP, OLE baseline, and end of OLE Period
- **Electrolytes (i.e., sodium, potassium, magnesium, and calcium):** Main Study baseline, each Main Study in-clinic scheduled visit, OLE baseline, OLE Week 12, and end of OLE Period
- **Urinalysis:** Main Study baseline, end of DB RWP, OLE baseline, and end of OLE Period
- **Pregnancy test:** serum at Main Study screening visit, urine at each Main Study in-clinic scheduled visit, serum at OLE screening visit, and urine at each OLE in-clinic scheduled visit
- **Drug screen:** Main Study screening visit, each Main Study in-clinic scheduled visit, OLE screening visit, and each OLE in-clinic scheduled visit
- **Alcohol screen:** Main Study screening visit, each Main Study in-clinic scheduled visit, OLE screening visit, and each OLE in-clinic scheduled visit

An authorized back-up laboratory may be used if necessary as an emergency laboratory. A list of laboratory assessments to be included in the outputs is included in APPENDIX 5.

See section 6.3 for handling of retests and unscheduled measurements.

Laboratory results will be reported in SI Units.

For **hematology, serum chemistry, electrolytes** and **urinalysis data** the following summaries will be provided across all study periods by visit:

- Observed and change from baseline (Main Study baseline and OLE baseline) for quantitative measurements
- Observed for qualitative measurements

- Shift table from baseline (Main Study baseline and OLE baseline) according to normal reference range criteria (for quantitative measurements)

The same summaries will be repeated on the RWP SAF by treatment group.

For hematology, serum chemistry, electrolytes and urinalysis data, the summaries of change from baseline during the OLE will differ depending on subjects:

- For rollover subjects: change from baseline = OLE measurements – Main Baseline
- For re-entry subjects: change from baseline = OLE measurements – OLE Baseline

For electrolytes, a box plot of change from baseline will also be provided by pre-randomization group across all study periods based on the SAF.

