#### **9.9.3. ECG EVALUATIONS**

A standard 12-Lead ECG will be recorded with the subject resting in supine for at least 5 minutes. ECGs will be performed during the Main Study screening visit, end of the DB RWP visit (or at early termination), OLE screening visit, and end of OLE visit. Results from the central ECG Reading Centre will be included in the reporting of this study. The following ECG parameters will be reported:

- PR Interval (msec)
- RR Interval (msec)
- QRS Interval (msec)
- QT Interval (msec)

- QT Bazett's correction (QTcB) Interval (msec) [derived]
- QT Fridericia's correction (QTcF) Interval (msec) [derived]
- HR (beats per minutes [bpm])
- Axis (degree)
- Overall assessment of ECG:
  - o Normal
  - o Abnormal, Not Clinically Significant
  - o Abnormal, Clinically Significant

The following summaries will be provided for ECG data across all study periods::

- Observed and change from baseline (Main Study baseline and OLE baseline) by visit (for quantitative measurements)
- Incidence of markedly abnormal criteria by visit

All ECG parameters results will be listed over time.

A listing of subjects meeting markedly abnormal criteria as well as a listing of subjects with abnormal ECG overall assessment will also be provided based on the SAF.

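### The nearest-record rule usually keeps abnormal unscheduled ECG, vital-sign and laboratory values out of the by-visit safety tables, and the SAP plans no any-time count

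*SAP*

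**What the plan says.** SAP 6.3 summarizes scheduled assessments by nominal visit. For the rest, "Unscheduled and Early Termination visits will be mapped based on the scheduled Period Day of each visit", using the windows in Table 2. If a window holds more than one record, "then the non-missing one closest to the scheduled Period Day will be used in the analysis". The rule applies to all records, "including unscheduled, repeated, and retest assessments or measurements as well as early discontinuation data". Ties go to the earlier record: "If two observations are equidistant from the scheduled Period Day, then the non-missing observation with the earliest collection date will be used". The value itself plays no part. Listings show every record.

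The tables that depend on this selection are:

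- ECG (SAP 9.9.3) and vital signs (SAP 9.9.4): "Incidence of markedly abnormal criteria by visit".
- Laboratory (SAP 9.9.2), among summaries given by visit: "Shift table from baseline (Main Study baseline and OLE baseline) according to normal reference range criteria". This section sends the reader to 6.3 for retests and unscheduled measurements.

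For ECG and for hematology and chemistry other than electrolytes, Table 2 has one Main Study window, "Study Day 1 < Period Day ≤ Date of Visit 16", with scheduled Period Day 15. It has one extension window, ending at Visit 33. For the across-period safety summaries, SAP 9.9 adds: "Data collected while subjects randomized to placebo were on placebo will be excluded from this summaries".

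**The concern.** Choosing one record by closeness to schedule suits observed values and mean changes by visit, because it stops extra testing from weighting the average. It does not suit a table meant to show who crossed a safety limit. Protocol 7.1 lets the investigator call an unscheduled visit whenever one is thought necessary, and repeat tests are often done because a result looked wrong. A rule that prefers the scheduled value then tends to set aside the records most likely to be abnormal.

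The error can go only one way relative to a subject-level count. A subject with an abnormal selected record is also abnormal on all records, but the reverse need not hold. Protocol 9.11.2 plans to tabulate how many subjects, and what percentage, pass set QT limits. Counting only the selected records can fall short of that number. SAP 3.6, which lists departures from the protocol, does not mention it.

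**Working it through.** The documents give no figure for this point, so there is none to reproduce. The check applies the SAP 6.3 rule to the Table 2 windows.

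**Inputs.** Nominal day s and window limits come from SAP Table 2. The allowance of up to 3 days after the nominal day comes from Protocol Appendix 1. The scheduled record falls on day v = s + k, with k = 0, 1, 2 or 3. An unscheduled record falls on another day d.

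**Rule.** The unscheduled record is used if |d − s| < |v − s|, or if the distances are equal and d < v. With v = s + k, the qualifying days run from s − k to s + k − 1, which is 2k days: 0, 2, 4 or 6. Where the window ends at the visit itself, its last day moves with the visit.

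| Window | s | Days selected, visit on time | Days selected, visit 3 days late |
|---|---|---|---|
| Vital signs, Week 4 (days 19–43) | 29 | 0 of 24 | 6 of 24 |
| Vital signs, end of double-blind period (from day 2) | 15 | 0 of 13 | 6 of 16 (days 12–17) |
| Vital signs, extension Week 12 (days 2–127) | 85 | 0 of 125 | 6 of 125 |
| ECG and non-electrolyte laboratory, Main Study (study days 2–113, assumed) | 113 | 0 of 111 | 6 of 114 |
| ECG and non-electrolyte laboratory, extension (from day 2) | 169 | 0 of 167 | 6 of 170 |

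These are counts of days, not probabilities; unscheduled tests need not be spread evenly over a window.

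**Example (hypothetical).** QTcF is above 500 msec at an unscheduled ECG on double-blind day 8, and the Visit 16 ECG on day 15 is normal. The distances are |8 − 15| = 7 and |15 − 15| = 0. Visit 16 is selected and the incidence table shows no event.

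**The Main Study ECG and laboratory window.** Its lower bound is written as Study Day 1, while most other cells in that row start at Period Day 1. This suggests that the window covers the whole Main Study: 16 weeks × 7 = 112 days, with Visit 16 due on study day 113. That is an inference, because the cell mixes Study Day and Period Day. If the window covers only the double-blind period, an unscheduled ECG during titration or the Stable-Dose Period has no window, since those cells are marked not applicable. It would then reach no by-visit table even when it is the only record.

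**Placebo arm, across-period summaries.** Take a subject with an abnormal unscheduled ECG on JZP-258 and a Visit 16 ECG on placebo, with the window covering the whole Main Study.

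- If on-placebo data are removed first, Visit 16 is gone and the on-JZP-258 ECG is used.
- If the record is selected first, Visit 16 is normally selected and then removed, so neither ECG is used.

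The SAP does not state the order.

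**The case against.** The strongest reply has four parts.

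- **Loss is not automatic.** A reader might infer that Visit 16 always wins and that every unscheduled value is dropped. The documents do not support that. A record that is alone in its window is used. So is one nearer the nominal day than a late visit, or one that ties and is earlier. Vital signs and electrolytes also have several Main Study windows.
- **The values are not hidden.** A reader might infer that a dropped abnormality leaves no trace in any table. Protocol 6.13.1 makes clinically significant adverse ECG and laboratory changes adverse events, and Protocol 6.13.5 requires the specified liver-test elevations to be recorded as such, so these should reach the treatment-emergent adverse event tables. All records are listed, and SAP 9.9.2 to 9.9.4 add listings of abnormal or markedly abnormal subjects.
- **A by-visit incidence describes the visit.** Protocol 9.11.2 itself frames vital-sign summaries by scheduled visit, its QT sentence does not say any time, and safety is descriptive.
- **The table shells are not available.** SAP 8 says they define table content, so an any-time row there cannot be ruled out.

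The first two parts limit the claim and stand. They do not replace the missing count: adverse-event tables depend on investigator judgment, Protocol 6.13.1 does not name vital signs in that rule, and listings give no incidence. The third part is fair for vital signs by visit. The QT sentence, however, concerns subjects exceeding limits and is not tied to a visit. The fourth part leaves an uncertainty, but the SAP text specifies no such row.

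**Conclusion.** The point holds as a gap in the safety tables. Under the SAP text, an abnormal unscheduled or repeat value is usually not counted when a scheduled value in the same window lies nearer the nominal day. With the scheduled visit on its nominal day, records from other days are never selected; with the visit 3 days late, records on 6 days can be. The effect is largest for ECG and non-electrolyte chemistry and hematology, with one window each in the Main Study and the extension. For laboratory data the affected outputs are shift tables, since the SAP plans no laboratory incidence table.

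The day counts for the Main Study ECG and laboratory window assume that it spans the whole Main Study. The number of subjects affected is unknown, because the documents give no rate of unscheduled tests or abnormal values.

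A reader might also infer that on-drug abnormalities in the placebo arm are certain to be lost from the across-period tables. The documents show only an unstated order of operations. If selection comes before exclusion, such values can be lost from the across-period ECG and laboratory summaries; if exclusion comes first, this does not happen.

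**What to change.** - Keep the nearest-record rule for observed values and mean change by visit.
- In SAP 9.9.2 to 9.9.4, add an any-time row, based on the worst post-baseline value, to the markedly abnormal ECG and vital-sign tables and the laboratory shift tables. Use all scheduled, unscheduled, repeat and early-termination records. Give the row for each period, by treatment received in the double-blind period, so that an open-label JZP-258 value is not counted under placebo.
- State in SAP 9.9 that on-placebo records are removed before record selection in the across-period summaries.
- In Table 2, write the lower bound of the ECG and laboratory window on one day scale.

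The cost is SAP wording, a little programming and one more row per table. No new data are needed and the efficacy analyses do not change.
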